5. To estimate the dose on the dose response curve where additional maternal intake of thiamine (oral dose) no longer meaningfully increases maternal ETKac at 24 weeks postpartum, and assess whether this depends on the presence/absence of a genetic hemoglobin disorder.
6. To test for differences between the 4 randomised groups on human milk total thiamine at 4, 12, and 24 weeks postpartum.
7. To test for differences between the 4 randomised groups on maternal ThDP at 24 weeks postpartum, and assess whether this depends on the presence/absence of genetic hemoglobin disorder.
8. To test for differences between the 4 randomised groups on maternal ETKac at 24 weeks postpartum and assess whether this depends on the presence/absence of a genetic hemoglobin disorder.
9. To estimate usual household salt intake from mean fortnightly salt disappearance (weight lost, in g).
10. To estimate salt intake among a subset of 100 lactating women, their male partners (if applicable), and their children 24-59 months (if applicable) using observed weighed salt intake records.
11. To estimate sodium intake using 24 hr urinary sodium concentrations among a subset of 100 lactating women.
12. To test for differences between the 0 & 10 mg randomised groups on Composite Mullen and the 5 subscales of the Mullen at 24 and 52 weeks postnatally.
13. To test for differences between the 0 & 10 mg randomised groups on Visual Paired Comparison Novelty Score and the attention and processing speed subscales at 24 and 52 weeks postnatally.

14. To test for differences between the 0 & 10 mg randomised groups on the Language Preference Task Score at 24 and 52 weeks postnatally.
15. To test for differences between 0 & 10 mg randomised groups on oculomotor scores at 24 and 52 weeks postnatally.
16. To determine the effect of inflammation, as measured by C-reactive protein (CRP) and α -1-acid-glycoprotein (AGP) on maternal ThDP at 2 and 24 weeks postpartum, and infant ThDP at 24 weeks postnatal.

5. Study Design

This will be a double-blind, four-parallel arm randomized controlled trial, in which 320 women and their newborn infants will be enrolled. Each dyad will participate in the study between 2 and 24 weeks postnatal, a 22-week intervention period. The primary outcome measure is human milk thiamine concentrations at 24 weeks postpartum (see **Figure 1**). There are additional cognitive assessments at 12 months (52 weeks) postnatal.

[figure not shown]

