9.2 Fortnightly monitoring

Every two weeks between 2-24 weeks, a member of the research team will visit the participant in her home to distribute new blister packs and collect used blister packs (compliance measure). At this time the field staff will also ask a small number of questions about capsule compliance, selling or sharing of salt, and about infant and young child feeding (IYCF) practices (was the infant exclusively breastfed over the previous two weeks). The field staff will weigh the household salt container to assess salt disappearance, and will provide more salt to the household.

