9.3 Salt disappearance

At the initial home visit after randomization, field staff will check that the household has removed all salt from the home, and will distribute table salt in specialized study containers. Using calibrated scales (sensitive to 1 g), field staff will log the initial weight of the salt container(s). Participants will be asked to consume only salt provided by the study, and since Cambodian families eat from a common pot, they will be instructed for all family meals to be prepared using this salt. At each fortnightly monitoring visit, field staff will weigh the salt container(s) to determine household salt consumption from salt disappearance. In addition, field staff will ask women to confirm the household members eating from the common pot.

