The fortnightly salt disappearance study will yield household salt consumption, but does not allow us to make strong estimates of intra-household salt consumption, nor the consumption of salt more holistically (including from packaged foods, salt-containing condiments). This information will be important moving forward in order to calculate dosages for thiamine-fortified salt. Also, gathering information not only from lactating women, but also presumably high consumers (husbands) and very low consumers at risk of deficiency (children after the window of micronutrient powder consumption, so 24-59 months) is also vital for future fortification modelling. Therefore, we will collect supplemental information in a randomly selected subset of households (n=100) using observed weighed intakes and maternal urinary sodium concentrations (randomly selected from larger study, and a second day repeat in 75 households on non-consecutive days). The participant (mother), the husband/man in household aged 18-50 years, and a child between 24-59 months (husband/man and child will not be applicable in all households) will be enrolled in this sub-study. For the observed weighed intake sub-study, field staff will sit in the participants home from dawn through dusk, recording, at the individual level, intake for the 1-3 individuals for all table salt and salt-containing condiments (e.g. fish and soy sauces) consumed throughout the day. For the mothers only, we will assess 24-hour urinary sodium concentrations (25). The mother will be instructed to awake, void her urine, record the time, and then collect all urine over the next 24 hours into a provided container; the collection will end when the woman will attempt to void urine at the exact specified time, 24 hours after initiation of collection. The field staff will visit her home to weigh the full container and then take an aliquot for testing (the remaining urine can be discarded). The urine

sample will be placed in the 4°C fridge in Kampong Thom for <1 week before being transported the Pasteur Institute in Phnom Penh for storage at -20°C and subsequent batch analysis via potentiometry using ion selective electrode on an automated ABX PENTRA C400. We will model thiamine fortification of salt using the University of Iowa's Intake Monitoring, Assessment and Planning Program software (<http://www.side.stat.iastate.edu/imapp.php>).

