2.2 Secondary Objectives

1. To estimate the dose on the dose-response curve where 90% of the maximum average is reached in the following outcomes:
 - a. Infant thiamine diphosphate concentrations (ThDP) at 24 weeks postnatal
 - b. Human milk total thiamine concentration at 4 and 12 weeks postpartum
 - c. Infant transketolase activity coefficient (TKac) at 24 weeks postnatal
 - d. Maternal ThDP at 24 weeks postpartum
 - e. Maternal TKac at 24 weeks postpartumand assess whether this depends on the presence/absence of genetic hemoglobin disorder for the following outcomes:
 - a. Infant ThDP at 24 weeks postnatal
 - b. Infant TKac at 24 weeks postnatal
 - c. Maternal ThDP at 24 weeks postpartum
 - d. Maternal TKac at 24 weeks postpartum
2. To test for differences between the 4 randomised groups on:
 - a. Human milk total thiamine at 4, 12, and 24 weeks postpartum
 - b. Maternal ThDP at 24 weeks postpartum
 - c. Maternal TKac at 24 weeks postpartum

and assess whether this depends on the presence/absence of genetic hemoglobin disorder for the following outcomes:

- a. Maternal ThDP at 24 weeks postpartum
- b. Maternal TKac at 24 weeks postpartum
3. To estimate the usual household salt intake from mean fortnightly salt disappearance (weight lost, in g).
4. In a subset of 100 lactating women, to estimate:
 - a. Salt intake of lactating women, their male partners (if applicable), and their children 24-59 months (if applicable) using observed weight salt intake records
 - b. Sodium intake using 24 hr urinary sodium concentrations in lactating women
5. To test for differences between the 0 mg and 10 mg treatment groups on the following outcomes at 24 and 52 weeks postpartum:
 - a. Composite and 5 subscales of Mullen
 - b. VPC Novelty score and the attention and processing speed subscales
 - c. Language Preference Task scores
 - d. Oculomotor scores
6. To determine the effect of inflammation, as measured by C-reactive protein (CRP) and α -1-acid glycoprotein (AGP) on the following outcomes:
 - a. Maternal ThDP at 2 and 24 weeks postpartum
 - b. Infant ThDP at 24 weeks postnatal

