7.3.6 Household salt intake

- Outcome: Continuous outcome of total salt consumption (g) in one day.
- Primary analysis: Descriptive means and standard deviation (overall and by number of individuals in the household) of total salt consumption within a day in a subset of 100 households.
- Secondary analysis: Descriptive means and standard deviation of the difference in salt intake, and intraclass correlation coefficient, between two days in a subset of 75 households.

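### SAP 7.3.6 specifies a one-day salt total in 100 households, although objective 3 asks for mean fortnightly disappearance; no Section 7 entry uses the fortnightly container weights

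*Combined protocol and SAP*

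**What the plan says.** SAP 2.2, objective 3, reads "To estimate the usual household salt intake from mean fortnightly salt disappearance (weight lost, in g". Protocol Section 4, secondary objective 9, says the same: "To estimate usual household salt intake from mean fortnightly salt disappearance (weight lost, in g". Protocol 1.2 makes household salt disappearance one of the trial's three objectives.

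The procedures match that definition. Protocol 9.3: "At each fortnightly monitoring visit, field staff will weigh the salt container(s) to determine household salt consumption from salt disappearance". Protocol 9.2: "The field staff will weigh the household salt container to assess salt disappearance, and will provide more salt to the household". Neither section limits the weighing to a subset of households.

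Protocol 9.3 then adds a sub-study, introduced with "we will collect supplemental information in a randomly selected subset of households (n=100) using observed weighed intakes" and with a repeat day in 75 households. Field staff observe for a day, "recording, at the individual level, intake for the 1-3 individuals for all table salt and salt-containing condiments". The SAP gives this work its own objective, 4a: "Salt intake of lactating women, their male partners (if applicable), and their children 24-59 months (if applicable) using observed weight salt intake records".

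The introduction to SAP Section 7 says that the section gives the details of every outcome analysed for the Section 2 objectives. Its one entry headed household salt intake, 7.3.6, takes salt consumed in one day as the outcome and reports the mean and SD of "total salt consumption within a day in a subset of 100 households", overall and by household size. It adds the between-day difference and intraclass correlation in 75 households.

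**The concern.** The objective and the analysis entry name different quantities. An analyst who follows 7.3.6 literally will report a one-day figure from the sub-study under the heading of household salt intake, and will have no instruction for the container weights collected throughout the intervention.

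What is missing is the derivation: how intervals are averaged, how top-ups enter the calculation, and whether missed weighings are imputed. Protocol 3.7 names usual salt intake, alongside dose, as information needed to formulate a fortified salt, so readers will look for this estimate.

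**Working it through.** The plan states no figure to reproduce here. The check is a comparison of text, followed by simple counts.

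**1. The two definitions side by side**

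| Feature | SAP objective 3, with protocol 9.2 and 9.3 | SAP 7.3.6 |
|---|---|---|
| Quantity | Container weight lost per fortnight | Total salt consumed in one day |
| Households | No subset named; 320 dyads enrolled | 100, with a second day in 75 |
| People covered | Everyone eating from the common pot | Not stated; the sub-study observes 1-3 people |
| Salt covered | Study table salt | Not stated; the sub-study also records salty condiments |

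**2. Could one day mean fortnightly loss divided by 14?** No. Weighing is not restricted to 100 households. The comparison between two days in 75 households also matches the sub-study's repeat day on non-consecutive days, and nothing in the fortnightly scheme.

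**3. Is the analysis elsewhere in the SAP?** Entry 7.3.7 is observed individual table salt over one day, and 7.3.8 is 24-hour urinary sodium. They follow 7.3.6 in the same order as objectives 4a and 4b follow objective 3. The other entries in 7.2 and 7.3 concern milk, blood and cognitive outcomes. SAP 6.3 draws on the fortnightly monitoring sheet, but only for capsule counts. No Section 7 entry uses the container weights.

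**4. Counts.** Inputs: 320 dyads (protocol 1.7), a 22-week intervention (protocol 1.5), and 100 and 75 households (SAP 7.3.6).

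- Intervals per household: 22 / 2 = 11.
- Maximum household-fortnights, before attrition and missed visits: 320 × 11 = 3,520.
- Household-days used by 7.3.6: 100 + 75 = 175.
- Households outside 7.3.6: 320 − 100 = 220, and 220 / 320 = 69%.

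**5. Why a derivation rule is needed.** Protocol 12.5 allows fortnightly visits ±2 days. Assume that this window applies to every weighing.

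- One interval can last from 14 − 4 = 10 to 14 + 4 = 18 days, so raw loss can differ from a true 14-day loss by up to 4 / 14 = 29% at constant use.
- With all 11 intervals observed, the inner visit dates cancel. Total time is 11 × 14 = 154 days, give or take 4, so the household mean is off by at most 4 / 154 = 2.6%.

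Standardising for days elapsed therefore matters little for complete households and more where intervals are missing.

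**The case against.** **Section 7 does not number its entries by objective.** The 100/75 analysis could be an objective 4 analysis under a misleading heading, with the objective 3 entry simply left out. This stands as a caution about intent. A reader might infer that the team deliberately replaced fortnightly disappearance with one-day intake; the documents do not show that. On either account the container weights have no entry and the heading does not match its content.

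**Much is specified elsewhere.** Objective 3 gives the summary and the unit. SAP 5.2 and 5.4 set an intention-to-treat default without exclusions for deviations, SAP 5.3 sets a general rule of multiple imputation with unimputed data as sensitivity, and the introduction to Section 7 calls for 95% confidence intervals. These provisions narrow the gap, although none mentions salt and none covers top-ups or averaging over fortnights. A reader might infer that objective 3 has no prespecification at all, or that reporting disappearance would be post hoc under SAP 4.2. Neither follows, because the summary is stated in advance in both documents.

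**The subset is randomly selected.** This is correct: leaving out 220 households does not by itself produce bias, and the 69% should not be read as an error size.

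**Disappearance has limits of its own.** Protocol 9.3 says that it cannot give strong within-household estimates and misses packaged foods and condiments. That justifies adding the sub-study. It does not make the sub-study the analysis of objective 3, and individual intake and urinary sodium already have their own entries.

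**Conclusion.** The point holds: objective 3 and SAP 7.3.6 must be reconciled. Objective 3 asks for mean fortnightly disappearance, 7.3.6 specifies a one-day total from a sub-study that observes 1-3 people per household, and Section 7 never uses the container weights.

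The consequence is limited to a secondary, descriptive objective with no treatment comparison. The primary milk thiamine analysis is unaffected, and the weighings are planned in any case. The 220 households and the maximum of 3,520 household-fortnights count data that 7.3.6 leaves unused. The documents give nothing from which to estimate how far the one-day and fortnightly figures would differ, so no numerical error is claimed.

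The conclusion rests on reading the 100 and 75 households as those of the protocol 9.3 sub-study, which the matching numbers and the repeat day support.

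**What to change.** Amend the SAP as follows.

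- **7.3.6 outcome.** Per household, mean container weight lost in g per 14 days: 14 × (sum of weight lost over the intervals) / (sum of days in those intervals). Weight lost in an interval is the weight after refill at one visit minus the weight before refill at the next. This keeps the unit of objective 3; dividing by 14 gives g/day as an equivalent rescaling.
- **7.3.6 analysis.** All enrolled households: mean, SD and 95% CI, overall and by number sharing the common pot.
- **Missing weighings.** Say whether the multiple imputation rule of SAP 5.3 applies or whether only observed intervals are used.
- **One-day analysis.** Move the 100/75-household analysis to a separate entry under objective 4. State whether its total covers the whole household or only the people observed, and whether condiments count.
- **Optional.** A sensitivity analysis omitting fortnights with reported selling or sharing of salt, which protocol 9.2 already records.

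The cost is SAP wording and a short derivation rule. No new data collection is needed provided that the amount of salt added, or the post-refill weight, is logged at each visit. Protocol 9.3 logs the initial container weight, but neither 9.2 nor 9.3 states that top-ups are recorded. Confirm this against the fortnightly data collection sheet; if they are not recorded, one field must be added.

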7.3.7 Individual salt intake

- Outcome: Continuous outcome of individual table salt intake (g) measured throughout one day by field staff.
- Primary analysis: Descriptive means and standard deviation of salt intake for a subset of 100 lactating women, their male partners (if applicable), and their children 24-59 months (if applicable).

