7.3.8 Sodium intake

- Outcome: Continuous outcome of urinary sodium concentration (mmol/24 hours) in lactating women.
- Primary analysis: Descriptive means and standard deviation of urinary sodium concentration in a subset of 100 lactating women.

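### SAP 7.3.7 reports only a one-day mean and SD of individual salt intake and leaves the second day in 75 households unused, so the spread of usual intake goes unestimated

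*Combined protocol and SAP*

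**What the plan says.** SAP 7.3.7 defines the outcome as "Continuous outcome of individual table salt intake (g) measured throughout one day by field staff". The analysis is "Descriptive means and standard deviation of salt intake for a subset of 100 lactating women", and likewise for male partners and for children aged 24-59 months where the household has them. No second-day analysis is listed.

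Protocol 9.3 sets up the sub-study in 100 randomly selected households, using observed weighed intakes and maternal urinary sodium, with "a second day repeat in 75 households on non-consecutive days". Field staff work by "recording, at the individual level, intake for the 1-3 individuals for all table salt and salt-containing condiments", so the repeat day yields person-level data.

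The only SAP analysis of the second day is in 7.3.6, for the household total: "Descriptive means and standard deviation of the difference in salt intake, and intraclass correlation coefficient, between two days in a subset of 75 households". SAP 7.3.8, on urinary sodium, plans "Descriptive means and standard deviation of urinary sodium concentration in a subset of 100 lactating women" and mentions no repeat.

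On purpose, protocol 3.7 names the usual salt intake of lactating women as a gap in knowledge and makes usual salt intake one of the two inputs needed to formulate the fortified salt. Protocol 9.3 justifies the sub-study by the need to see how intake differs between household members, with husbands as presumed high consumers and young children as very low consumers, and says fortification will be modelled in named intake-planning software. Neither document says how the repeat day enters that modelling, and the SAP does not mention the modelling.

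**The concern.** Usual intake is a person's long-run average. One observed day equals that average plus that day's departure from it. The SD across persons of one-day values therefore mixes differences between people with variation from day to day, and it exceeds the SD of usual intake whenever the second part is not zero. One day per person cannot separate the two parts. Two non-consecutive days in some of the same people can, and the protocol already collects them.

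The household ICC in 7.3.6 does not fill the gap. It describes the household total, whose day-to-day variation need not match that of a woman, a man or a child.

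At stake is a description. A reader who takes the SD from 7.3.7 as the spread of usual intake would think women, men and children differ more among themselves than they do, and would place too many of them at very low or very high intakes. That matters for a fortification level meant to serve low and high consumers alike.

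**Working it through.** The documents give no SD, ICC or precision for individual salt intake and no derivation of the 100 or the 75, so there is no stated figure to reproduce.

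**Inputs from the documents.** 100 households; 75 with a second non-consecutive day (protocol 9.3); one day analysed per person (SAP 7.3.7).

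**Inputs assumed.** The person-level ICC, meaning the between-person share of the one-day variance, taken over 0.3 to 0.9. Normal data for the tail shares and the simulation.

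**Step 1: spread.** Var(one day) = between-person variance + within-person variance. With ICC = between/(between + within), SD(one day)/SD(usual) = 1/sqrt(ICC).

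| Assumed ICC | 1/sqrt(ICC) |
|---|---|
| 0.9 | 1.05 |
| 0.7 | 1.20 |
| 0.5 | 1.41 |
| 0.3 | 1.83 |

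**Step 2: what it would mean in the tails.** Under normality, the share of one-day values outside the 5th to 95th percentiles of usual intake is 2 × Phi(-1.645 × sqrt(ICC)). This gives 0.169 at ICC 0.7, 0.245 at 0.5 and 0.368 at 0.3, against 0.10 for usual intakes themselves. Intake cannot fall below zero, so these shares are only a guide, least of all for the lower tail in children.

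**Step 3: can the planned repeats separate the parts?** In repeated persons, within-person variance = Var(day 1 - day 2)/2, and SD(usual) = sqrt(Var(day 1) - within-person variance). In a simulation with 100 persons, 75 repeats and 4,000 runs, the median of estimated over true SD(usual) was about 1.00 at each ICC. The 95% ranges were:

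- ICC 0.7: 0.78 to 1.20
- ICC 0.5: 0.68 to 1.26
- ICC 0.3: 0.07 to 1.43

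Men and children will be fewer. At ICC 0.5, with assumed sizes of 40 persons and 30 repeats, the range was 0.39 to 1.41. With 20 persons and 15 repeats it was 0 to 1.56, and the between-person variance came out non-positive in about 5% of runs.

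**Step 4: gain for the mean.** Set the one-day variance to 1. A person with one day contributes information 1. A person with two days has a mean with variance (1 + ICC)/2 and contributes 2/(1 + ICC). For women the total is 25 + 75 × 2/(1 + ICC), against 100 from one day each.

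| Assumed ICC | Information | SE ratio = sqrt(100/information) | Reduction in SE |
|---|---|---|---|
| 0.7 | 113.2 | 0.940 | 6% |
| 0.5 | 125.0 | 0.894 | 11% |
| 0.3 | 140.4 | 0.844 | 16% |

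**The case against.** The strongest reply is that nothing in 7.3.7 is miscalculated. The outcome is labelled as one day's intake, and the matching objectives (protocol section 4, objective 10; SAP 2.2, objective 4a) speak of salt intake without calling it usual. In the objectives, usual intake belongs to the household figure from fortnightly disappearance. This stands. A reader might infer that the SAP reports a wrong SD, but the documents do not support that: the SD is right for the quantity named. What remains is that protocol 3.7 asks for usual intake among lactating women, and no SAP analysis of individuals gives its spread.

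A reader might also infer that the one-day SD will distort the fortification modelling or misplace people in the tails. The documents do not support this either. 7.3.7 plans no percentile, cut-off or prevalence, and nothing says its SD feeds the modelling. The software named in protocol 9.3 may use the repeat day. Since neither document says, neither reading can be shown, and the supportable request is that the SAP state it.

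Three further points stand. The mean is not biased by using one day. The size of the excess rests wholly on assumed ICCs. The variance components could be poor for men and children, who are not present in every household.

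The extension to urinary sodium is less secure. The parenthesis in protocol 9.3 can be read as repeating both measures, but the urine procedure itself describes a single 24-hour collection.

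**Conclusion.** The point holds as a gap, not an error. The individual analysis leaves unused a second day of person-level data that the study will already have, and the one-day SD it reports is wider than the spread of usual intake by 1/sqrt(ICC). The direction is certain for any day-to-day variation. The size is not known: it is 5% at an assumed ICC of 0.9 and 83% at 0.3. Reading the same ratio across to percentiles also requires the one-day and usual-intake distributions to share a shape.

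This is a minor matter in a secondary, descriptive outcome. It involves no hypothesis test and does not touch the milk thiamine dose-response result. It is worth acting on because the data are already planned and the summary bears on a stated aim of the study.

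**What to change.** In SAP 7.3.7, keep the one-day mean and SD and add a random-intercept model fitted to all person-days, separately for women, men and children. Report the mean and the within- and between-person SDs with confidence intervals. Give percentiles of usual intake only where the number of repeats supports them, which means women first, and state the transformation or distribution assumed.

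In 7.3.8, state whether the 24-hour urine collection is repeated. If it is, add the same model there.

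Add a sentence saying how the repeat day enters the fortification modelling planned in protocol 9.3.

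The cost is a little more analysis and a distributional assumption. No new data are needed. The variance components will be imprecise if the ICC is low or the male and child groups are small, and the confidence intervals will show this.
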